
2.4 Potential Risks and Benefits

2.4.1 Potential Risks

2.4.1.1 Risk from mydriatics

Instillation of dilating eye drops is required prior to the indirect and direct ophthalmoscopy. The side effects of blurred vision and photophobia are not expected to trouble these particular participants (who will be unconscious), and the risk of acute narrow angle closure glaucoma (a rare side-effect of mydriatics) is very low in the pediatric population. Cardiovascular effects have been reported in premature infants, who are not candidates for enrollment. The dilating effect of mydriatics generally dissipates within 2 hours of instillation.

2.4.1.2 Hypertonic saline

The known side-effects of hypertonic saline include:

- Hypernatremia
- Hypokalemia
- Rebound cerebral edema upon termination of therapy

These conditions are all a direct result of the increased sodium and osmolarity that are also the goal of the intervention. Assiduous monitoring of electrolytes (as described in 9.2.4) will therefore be undertaken to balance desired effects with possible side effects.

2.4.1.3 Assisted ventilation

Mechanical ventilation via an endotracheal tube has a number of associated risks which can be broadly classified into following categories²⁴⁶

- Adverse effects of positive pressure, volume and flow:
 - Pneumothorax
 - Pneumomediastinum
 - Hypotension
 - Bronchospasm
 - Pulmonary hemorrhage
- Adverse effects of endotracheal intubation
 - Endotracheal tube obstruction
 - Inadvertent endotracheal tube dislodgment
 - Bradycardia induced by vagal response
 - Mucosal inflammation
 - Stridor
 - Subglottic stenosis
 - Respiratory nosocomial infections

These events may be persistent and severe, necessitating tracheostomy.

2.4.2 Known Potential Benefits

Participants will have the benefit of the increased level of nursing care provided on the PICU and PRW. Were they not to be enrolled in this study, they would be hospitalized in the general pediatrics ward at QECH. The general ward is staffed by government employed nurses. The patient to nurse ratio is often $> 50:1$. In contrast, the PRW patient to nurse ratio is 2:1 at maximum and is 1:1 in the PICU. The diligent observations and monitoring that are provided on the PRW and in the PICU are impossible in the general ward. For a disease such as CM that demonstrates rapid progression, extreme clinical vigilance and the ability and resources to respond to clinical needs are crucially important. These can only be provided on the PRW/PICU and serve as the major benefit of participants to this study – independent of any benefit provided by the investigational efforts. When the guardians of potential study participants decide against providing consent, the patients are eligible to receive the “usual care” (sans study-specific investigations) on the PRW.

3 OBJECTIVES

3.1 Study Objectives

Primary Objective

Compare final outcomes in pediatric CM patients receiving usual care (Arm 3) with both of two interventions (Arm 1 and Arm 2).

Secondary Objectives:

1. Among survivors of this interventional study, compare rates of adverse neurological outcomes in those assigned to the two interventions and those assigned to usual care.
2. Among all children admitted to the PRW with CM whose parents consent to screening, evaluate and validate biomarkers of increased brain volume.
3. Assess the safety of early intubation and mechanical ventilation as well as intravenous hypertonic saline in children with CM.
4. Establish association between specific pathogenic mechanisms and TCD-derived phenotypes.
 - a. microvascular obstruction phenotype with MRI findings
 - b. hyperemia phenotype with hypercapnia on blood gas analysis, acidosis, and seizures on EEG
 - c. vasospasm phenotype with regional EEG findings of loss of fast frequencies and increased slow frequencies in territories of affected vessels and MRI findings with localized ischemic changes
 - d. low flow phenotype with compromised hemodynamics, diminished compensatory reserve and increased brain volume per MRI

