2.1.13 Hypothesis

Description of the Study Refining the standard clinical case definition of CM to include malarial retinopathy may improve specificity and focusing on retinopathy-positive CM participants with moderately severe increased brain volume identifies the group at highest risk of dying.

Our data suggest that these children experience a disruption of the respiratory control center manifesting as a respiratory arrest. The final cause of death appears to be respiratory arrest secondary to intracranial hypertension.

Hypothesis: Death in children with CM occurs when raised intracranial pressure from severely increased brain volume impairs the function of the medullary respiratory center; interventions which reduce brain volume or support ventilation will improve survival rates in CM patients.

Using numbers derived from the ongoing studies in Malawi, of 100 children who meet the standard clinical case definition of CM, approximately 70-75 will be retinopathy-positive. Of these, ~ 47% (34-35 children) will have severely increased brain volume on MRI, and, with the observed mortality rate of 37% in this clinical subset, about 12 of these children will die. The majority recover quickly and completely, suggesting that the adverse effects of increased brain volume on respiratory status are reversible and short-lived⁵².

All CM patients enrolled in the study will contribute to the evaluation of surrogate markers of brain volume.

CM patients who are retinopathy-negative and who have evidence of increased brain volume on MRI will be eligible to be enrolled in an identical interventional study (of assisted ventilation or hypertonic saline). This group, when combined with the retinopathy-positive CM patients described above, represents children who satisfy the less stringent but standard WHO definition of cerebral malaria⁸¹. In order to increase generalizability of our study results, we will analyze data from this combined group, but perform a sensitivity analysis to determine if treatment effects vary in children of different retinopathy status.

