2.3 Rationale

This clinical trial of adjuvant therapy (immediate ventilatory support, or hypertonic saline) for Malawian children with CM is directed toward the supportive treatment of increased brain volume, and it avoids the pitfalls that have bedeviled previous trials because:

- The interventions target a mechanism recently recognized as being strongly associated with a fatal outcome, severely increased brain volume; this mechanism is self-limited in CM survivors, suggesting that supportive care or rescue therapy may be effective.

The clinical trial setting in Malawi has been transformed because, beginning in July 2017, mechanical ventilation became available in the new Paediatric Intensive Care Unit (PICU) at the Queen Elizabeth Central Hospital.

This introduces new ethical issues: mechanical ventilation cannot be withheld in patients who suffer a respiratory arrest, and ventilatory support may result in a cadre of survivors with severe neurological sequelae. Therefore, “treatment failure” (failure of the primary intervention) is defined differently in the different therapeutic arms. In Arms 2 and 3, in which participants are not randomized to immediate ventilatory support, any participants who suffer respiratory arrest and are placed on ventilators *or* who die *or* are brain dead will be classified as treatment failures. In Arm 1, the patients who are randomized to receive immediate ventilatory support, “treatment failure” is defined as brain death at any time, *or* death at 7 days, with ventilatory support withdrawn.

The hypothesis underlying this prospective, randomized clinical trial is that death in children with CM occurs when raised intracranial pressure from severely increased brain volume impairs the function of the medullary respiratory center and that interventions which reduce ICP or support ventilation will improve survival rates in CM patients.

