3.2.2 Secondary Outcome Measures

1. Neurological sequelae in survivors, assessed at 1, 6, and 12 months after randomization via the Malawi Developmental Assessment Tool (MDAT) for participants up to the age of 59 months old, and the Kaufman Assessment Battery for Children, Version II (KABC II) for participants over the age of 59 months. All survivors will also be assessed using the Glasgow Outcome Scale (GOS)²⁴⁷. The GOS is a global scale for functional outcome that rates patient status into one of five

categories: dead, vegetative state, severe disability, moderate disability or good recovery.

2. Surrogate measures of increased brain volume: At the time of admission (only): opening CSF pressure, archived samples of blood, urine and CSF. Daily while comatose: ophthalmoscopy for papilledema (present/absent), optic nerve sheath diameter in mm, NIRS measurements of cerebral oxygenation and muscle reperfusion, standardized neurologic observations.
3. Standard TCD phenotypes: microvascular obstruction, hyperemia, vasospasm, low flow, isolated posterior hyperemia). Potential mechanisms: increased brain volume per MRI/ischemic changes, hypercapnia/acidosis/seizures, localized ischemia on MRI, compromised hemodynamics/diminished compensatory reserve/increased brain volume per MRI

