 - Continuous monitoring of heart rate and rhythm from EKG, respiratory rate, and pulse oximetry via monitor, and blood pressure via arterial line or cuff. Signals will be archived for offline analyses aimed at identifying heart rate variability patterns over time associated with CM and with clinical improvement or decline in association with treatment.

- Electrolytes and acid-base balance 3-hourly during the first 24 hours and 6-hourly thereafter (in those randomized to hypertonic saline)
- PRW and PICU
 - 2-hourly assessments of vital signs (including temperature) and Blantyre Coma Score until BCS = 5 and temperature is $\leq 37.5^{\circ}\text{C}$ for 24 hours, then 6-hourly.
 - 6-hourly assessments of malaria parasitemia and hematocrit, until two consecutive parasitemia counts are negative.
 - 12-hourly neurological examinations,
 - Daily ophthalmoscopy while unconscious
 - Daily ONSD measurements (while unconscious)
 - Daily TCD examinations
 - Daily MRI examinations (while unconscious if participant is clinically stable for transportation to undergo neuroimaging)

The primary objective (treatment success or failure) will be determined within the first 7 days of hospitalization (Figure 8)

Secondary objectives (Figure 8)

1. The secondary objective involving neurological sequelae at 1, 6, and 12 months after randomization will be determined in survivors randomized in the clinical trial.
2. The secondary objective of identifying surrogate measures of increased brain volume will include participants in the clinical trial as well as study subjects who are screened but do not meet inclusion criteria for clinical trial enrollment e.g. their brain volume is not increased enough to qualify for enrollment in the trial and are therefore not randomized.
3. The secondary objective of assessing the safety of early intubation and mechanical ventilation will include participants in the clinical trial as well as study subjects with CM who are screened but do not meet inclusion criteria for clinical trial enrollment e.g. their brain volume is not increased enough to qualify for enrollment in the trial and are therefore not randomized.
4. TCD endpoints will be determined on all participants (see section 7.2.2.4)]

Choice of participant population and sample size considerations

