Centralization of evaluations: MRI, ophthalmoscopy, ONSD, TCD, EEG, and neuro-checks will be carried out either at the bedside in the PRW/PICU or in the MRI suite.

Safety monitoring: A local independent safety monitoring team (ISM) will be appointed for the study. The team will consist of two local physicians with knowledge of the clinical setting and practices, but without direct involvement with this study. They will be notified of all SAEs and asked to comment on the relatedness of these events to the interventions. They will also be asked to review AEs at the discretion of the local investigators, IRBs, or the Data Safety and Monitoring Board (DSMB).

A DSMB is justified for this study for two reasons: (1) the anticipated mortality in this group of gravely ill children, without adjunctive treatment, is over 30% (2), and serious adverse events have been reported for HPS (Section 2.3.1.2) and assisted ventilation (Section 2.3.1.3). Interventions may result in survival of children who would have otherwise died, and some of these children may be severely neurologically impaired. In a country like Malawi where there is no social support for such children and their families, their survival could create a burden for the family which might worsen stress and social problems.

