9 ASSESSMENT OF SAFETY

9.1 Specification of Safety Parameters

The primary safety parameter for this study is a comparison of survival of the participants in the three treatment arms. In addition, we will be assessing long term neurological sequelae for all participants.

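### Secondary objective 1 compares neurological sequelae among survivors only in a trial meant to change survival; add a three-state comparison (dead, alive with severe sequelae, alive without) in all randomised children

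*Combined protocol and SAP*

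**What the plan says.** The survivor restriction appears wherever the objective is defined. The Protocol Summary and section 3.1 have "Among survivors of this interventional study, compare rates of adverse neurological outcomes" "in those assigned to the two interventions and those assigned to usual care". Section 3.2.2 defines the outcome as sequelae in survivors at 1, 6 and 12 months and applies the Glasgow Outcome Scale (GOS) to survivors. Section 4 says the objective "will be determined in survivors randomized in the clinical trial". Table 8 (section 11.5) and section 11.7 treat severe sequelae as a binary outcome with a logit link and give no rule for children who die.

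The trial's premise, in section 2.1.13, is that "interventions which reduce brain volume or support ventilation will improve survival rates in CM patients", and section 11.6 targets a 50% relative reduction in mortality. Section 4 (safety monitoring) adds: "Interventions may result in survival of children who would have otherwise died, and some of these children may be severely neurologically impaired". Section 2.3 warns that "ventilatory support may result in a cadre of survivors with severe neurological sequelae". That sentence follows from the point that ventilation cannot be withheld after a respiratory arrest, and rescue ventilation is also given in Arms 2 and 3.

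Five places come close to a joint analysis:
- Section 4's outcome list refers to sequelae rates in all three groups, without a survivor restriction, and its data-collection text names the GOS, which has a category for death. It names no analysis.
- The primary outcome in section 4 counts severe irreversible neurologic failure together with death, but only within 7 days.
- Section 9.1 makes survival the main safety comparison and then says: "In addition, we will be assessing long term neurological sequelae for all participants". These are two separate items.
- Section 11.7.1 covers missing responses and is silent on death before a visit.
- Section 11.7.2 models treatment success jointly with survival, not with sequelae.

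**The concern.** Survival is a result of treatment. If an intervention works, its survivors include children who would have died under usual care (UC), and the UC survivors have no counterpart to them. Randomisation does not balance the two survivor groups. If the extra survivors do worse than the rest, the sequelae rate rises in the treated arm although no child was harmed. If they do better, it falls although no child was protected.

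The protocol's stated worry is how many of the children assigned to an arm end up dead, severely impaired, or alive without severe impairment. A survivor-only rate mixes how many were rescued with who was rescued. A reader could partly rebuild the answer from deaths and sequelae counts, but the visit, the cut-off and the contrast would then be chosen after the results were known, in an unmasked trial.

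**Working it through.** **The plan's own figure.** There is no sample size or power for this objective. The figure carrying the survival effect is the 38 VENT children in section 11.6, for mortality of 0.28 against 0.14, one-sided 5%, 80% power. It reproduces with the variance taken under the alternative: (1.645 + 0.842)² × 0.14 × 0.86 / 0.14² = 37.98, so 38. A large survival difference is therefore built into the design.

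**Inputs.**
- Mortality: 36% UC and 18% treated (section 11.5); 28% UC and 15.8% VENT, 3/19 (section 11.6).
- Assumed, not in the documents: severe-sequelae rate b = 20% in children who survive under either treatment, s = 10-60% in extra survivors, and no effect of treatment on the former.

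**Formulas**, with mortality m0 (UC) and m1 (treated):
- UC: alive with sequelae (1 - m0)b; alive without (1 - m0)(1 - b).
- Treated: alive with W = (1 - m0)b + (m0 - m1)s; alive without (1 - m1) - W.
- Survivor-only rate: b in UC, W/(1 - m1) in treated.

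Example at 36/18%, s = 60%: W = 0.64 × 0.20 + 0.18 × 0.60 = 0.236, and 0.236/0.82 = 28.8%, against 20% in UC.

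| Mortality UC/treated | s | Treated survivor-only rate (UC 20%) | Shift, points | Alive without, per 100 randomised | Alive with, per 100 randomised |
|---|---|---|---|---|---|
| 36/18% | 10% | 17.8% | -2.2 | 51.2 → 67.4 | 12.8 → 14.6 |
| 36/18% | 20% | 20.0% | 0 | 51.2 → 65.6 | 12.8 → 16.4 |
| 36/18% | 60% | 28.8% | +8.8 | 51.2 → 58.4 | 12.8 → 23.6 |
| 28/15.8% | 10% | 18.6% | -1.4 | 57.6 → 68.6 | 14.4 → 15.6 |
| 28/15.8% | 60% | 25.8% | +5.8 | 57.6 → 62.5 | 14.4 → 21.7 |

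**Other base rates.** Table 3 (section 2.1.12) gives 16-45% for sequelae of any severity, by Doppler group, in a wider cerebral malaria cohort. At 36/18% and s = 10-60%, b = 16% shifts the contrast by -1.3 to +9.7 points, and b = 45% by -7.7 to +3.3.

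**Why two differences are needed.** If every extra survivor were severely impaired (s = 100%, b = 20%, 36/18%), alive without severe sequelae would be 51.2 in both arms, a difference of 0. Alive with severe sequelae would rise from 12.8 to 30.8, a difference of +18.0.

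**Precision.** Randomised UC is 16 children, or 16 + 4 projected for 2023 = 20 (section 4, projected enrolment). The intervention arms are projected at 32, or 21 for VENT if stopped early (section 11.7). Unpooled binomial standard errors were taken over 36/18%, 28/14% and 36/26.3% mortality (26.3% is 5/19 in VENT in section 4, counting brain death), with b = 20% and s = 10-60%.

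| Sizes (UC v treated) | Survivor-only SE | 95% half-width, alive without | 95% half-width, alive with |
|---|---|---|---|
| 20 v 32 | 13-14 points | 27-28 | 19-21 |
| 16 v 21 | 15-17 points | 31-32 | 22-25 |

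Example at 20 v 32, 36/18%, s = 60%, alive without: 1.96 × √(0.512 × 0.488/20 + 0.584 × 0.416/32) = 27.8 points.

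**The case against.** The strongest case against is that this is a reporting suggestion on a secondary objective, with little to gain.

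- **Death is partly in view already.** Section 4 refers to sequelae in all three groups and names a scale with a category for death. That stands and narrows the gap: what is missing is an analysis line, not an instrument.
- **The warning in section 2.3 arises from respiratory arrest.** Rescue ventilation reaches Arms 2 and 3, so rescued, possibly impaired survivors can occur in UC as well. This stands. Section 4's safety text is the one that ties impaired extra survivors to the interventions.
- **The mortality inputs are not a randomised UC rate.** The 36% pools 48 historical controls, with scans from 2014-2017, and 16 randomised children; the 28% also rests on historical controls. Ventilation became available only in July 2017. Mortality in the 16 is not given separately. The real survival gap, and so the shift, may be smaller.
- **The illustrative range is lopsided.** It goes 10 points below the base and 40 above, so it leans towards apparent harm. A reader might infer that the survivor-only analysis will make treatment look harmful. The documents do not support that: the direction depends on an unknown rate in extra survivors.
- **Little inferential gain.** The half-widths exceed the illustrated differences. The 16 UC children were enrolled in 2018-2019, when hypertonic saline could not be imported. That arm had 3 children by the end of 2021, and UC has 0 projected for 2022 and 4 for 2023. That contrast is almost entirely non-concurrent.
- **Data at 12 months are not assured.** Sections 5.3.4 and 7.5 schedule withdrawn children only to about one month, and Appendix A has no vital-status item.

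The last two points limit what the added analysis can show and must be handled in the fix. None of them makes a survivor-only rate answer the question the protocol raises.

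**Conclusion.** The concern holds as a point about the estimand of a secondary objective. The plan compares sequelae only in groups that treatment helps to select, and no section combines death with later sequelae in all randomised children.

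The size is illustrative: -2.2 to +8.8 points at 36/18% mortality and -1.4 to +5.8 at 28/15.8%, under the assumed 20% base and 10-60% in extra survivors, and zero if those rates match. With that base every shift is below the survivor-only standard error of 13-17 points.

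Two stronger inferences fail. The primary result is not affected, because it has its own 7-day composite. Nor do the figures show that the survivor-only test would reach a false significant result. The added analysis is a cheap improvement, for estimation only.

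**What to change.** 1. Keep the survivor-only analysis and label it as conditional on survival.
2. Name one visit (for example 12 months). For all randomised children, tabulate by arm: dead, alive with severe sequelae, alive without severe sequelae.
3. For each intervention against randomised UC, report risk differences with 95% CIs for (a) alive without and (b) alive with severe sequelae.
4. Count every death up to that visit as dead, including deaths after day 7.
5. State the cut-off for severe; section 3.2.2 names the MDAT, KABC-II and GOS but gives none.
6. Record vital status at that visit for every randomised child, including those withdrawn, as far as consent allows. Treat only unknown status as missing under section 11.7.1.
7. State that the 48 historical controls are not included, although they count in the N of 128 in section 11.7.
8. State prominently that hypertonic saline v UC is almost entirely non-concurrent, and report the results as estimates without a test.

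The cost is SAP wording, one table, two risk differences per comparison and a vital-status item at one visit. The downside is wide intervals: about 27-32 points either side for (a) and 19-25 for (b). The change does not address unmasked outcome assessment.

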3.2 Study Outcome Measures

3.2.1 Primary Outcome Measures

Final outcomes will be determined within 7 days: treatment success or failure, where failure is a composite outcome of death, ventilatory rescue, and brain death. Final outcomes within 7 days in children who meet the standard WHO definition of cerebral malaria treatment success or failure, where failure is a composite outcome of death, ventilatory rescue, and brain death.

